1.2 Schema

Figure 1 Study Schema

CCI

1.3 Schedule of Activities

Study Period	Screening			Randomization and Treatment Period					Safety Follow-up		Discontinuation	
	CCI											
	CCI											
Window (days)	CCI											
Timing		Start of SC	Start of BC	Start of TRC1	CCI	Start of TRC2	Start of TRC3	Start of SFC	Day 14 after stopping intake of study medication	End of the SFC		
Informed Consent	X ^b											
Inclusion, Exclusion/Eligibility criteria	X	X	X	X ^c								
Demographics	X											
Medical History (includes current condition, eg, documentation of surgical diagnosis of endometriosis ^d)	X											
Gynecological History	X											
Prior/Concomitant Medications	X	X	X	X	X	X	X	X	X	X	X	

Study Period	Screening			Randomization and Treatment Period				Safety Follow-up			Discontinuation
CCI	CCI										
Window (days)	CCI										
Full Physical Examination (including height and weight)	X							X			X
Focused Physical Examination (Cardiac, Respiratory, GI)				X	X		X			X	
Gynecological Examination ^e / Contraception Counseling ^f	X							X		X	X
Rescue Medication Dispensing and Instructions for Use		X	X	X	X		X	X			
Home UPT Dispensing ^g	X		X	X							
Treatment Allocation				X							
CCI			X								
				X ^h	X ⁱ		X				
OG-6219/Placebo Accountability				X ^h	X		X	X			X
Dispense/Collect eDiary		X	X	X						X	X

Study Period	Screening	Randomization and Treatment Period						Safety Follow-up	Discontinuation	
CCI	CCI							CCI		
Window (days)	CCI									
eDiary Training/Re-training ^j		X	X	X	X		X	X		
eDiary Compliance ^k			X	X	X	X	X	X	X	
eDiary CCI										
				■				■		
Patients' Impression of Change (PGI-C) ¹						X	X	X		
Patients' Impression of their Overall Severity (PGI-S) ¹				X		X	X	X		

Study Period	Screening			Randomization and Treatment Period				Safety Follow-up			Discontinuation
CCI											
Window (days)	CCI										
Vital Signs (Heart Rate, Blood Pressure, Respiratory Rate, Temperature)	X	X	X	X	X		X	X		X	
12-Lead ECG	X			X ^m	X ^m		X ^m	X		X	X
Clinical Laboratory Tests (Hematology and Chemistry panels) ^a	X			X	X		X	X		X	X
Urinalysis	X			X	X		X	X		X	X
STI Panel ^o	X										
UPT ^p	X	X	X	X	X	X	X	X		X	X
Serum Pregnancy Test (β-hCG) ^q	X		X	X	X		X	X		X	X
CCI											
AE	X	X	X	X	X	X	X	X	X	X	X

Study Period	Screening			Randomization and Treatment Period					Safety Follow-up			Discontinuation
CCI	CCI					CCI	CCI					
Window (days)	CCI											
Plasma PK Sampling ^u											X	
CCI												
Columbia-Suicide Severity Rating Scale (C-SSRS) ^{1,7}	X	X	X	X	X		X	X		X	X	

Abbreviations: AE=Adverse event; BC=Baseline Cycle; CCI; C-SSRS=Columbia-Suicide Severity Rating Scale; CCI; DX=Day X; DYS=Dysmenorrhea; CCI; ECG=Electrocardiogram; eDiary=electronic diary; EHP-30=Endometriosis Health Profile-30; EOS=End of Study; EOT=End of Treatment; CCI; GI=Gastrointestinal; hCG=Human chorionic gonadotropin; HRQoL=Health-related quality of life; CCI; NMPP=Non-menstrual pelvic pain; CCI; OPP=Overall pelvic pain (endometriosis-related); PAP=Papanicolaou; CCI; PGI-S=Patient Global Impression of Severity; PK=Pharmacokinetic; CCI; PRO= Patient-reported outcome; SC=Screening Cycle; SFC=Safety Follow-up Cycle; CCI; STI= Sexually transmitted infection; CCI

CCI TRC1=Treatment Cycle 1; TRC2=Treatment Cycle 2; TRC3=Treatment Cycle 3; CCI UPT=Urine pregnancy test; VX=Visit X; CCI ; ~ = approximately.

- a. V1 is recommended to occur around bleeding day (menses).
- b. Screening may occur over several days after informed consent is signed.
- c. Recheck clinical status before randomization (CCI), and/or first dose of study treatment.
- d. Surgical diagnosis of endometriosis is confirmed by documentation in the medical records.
- e. Examination includes speculum insertion, bimanual examination, and breast examination. If a previous PAP smear report is available and the results meet the local guidelines, no additional tests are needed; otherwise, the PAP smear should be performed at Screening.
- f. Post-study contraceptive counseling (CCI); Participants who do not wish to conceive (CCI) should begin a new contraceptive method as soon as possible. Post-study contraceptive counseling will be provided by study site personnel in accordance with the SoA.
- g. The UPT is centrally provided. If any menstrual cycle delay is noted, the participant must immediately perform UPT and contact clinic to schedule a visit as soon as possible and the Sponsor must be contacted. Additional UPT can be dispensed as needed.
- h. C Participant must be CCI compliant with CCI to be randomized.
- i. A tablet count will be performed at C and open bottles returned to participants to complete Cycle 1 treatment.
- j. Participants will begin daily CCI completion at C. Investigator or designees should explain the importance of completing the eDiary CCI. Investigators are to evaluate participants compliance with the eDiary during screening to assess eligibility per inclusion criteria. Participants who are not complaint should be re-trained.
- k. Participant compliance with eDiary entries must be CCI during both the SC and the BC to be randomized (information to be provided by the eDiary portal).
- l. CCI
- m. ECG will be performed pre-witness dose and 1.5 hours after dose (witness dose), following the PK Sparse assessment.
- n. CCI
- o. If indicated, participants will be tested for gonorrhea and chlamydia unless they were screened within the past 3 months and have no new sexual partner. Testing for trichomonas and bacterial vaginosis will only be required if abnormal vaginal discharge is present. Testing will be performed locally and may be repeated during the study as needed.
- p. If local regulations indicate that UPT should be performed more frequently, follow local regulations where applicable.
- q. In addition to visits specified, serum pregnancy test also required any time pregnancy is suspected or if UPT is positive (unless pregnancy already confirmed by ultrasound).

CCI

- u. OG-6219 and active metabolite FOR-1011; blood samples for PK analysis will be collected at all visits during the dosing period including the EOT Visit and discontinuation. In addition, for the optional intensive PK sampling, a minimum of C participants per treatment group (incl. Placebo group) will be enrolled on CCI, for entire duration of the study. A complete schedule of PK assessment times is found in Table 8. The witness dose should be administered at site for CCI.

- v. **C** sample collection to be collected within 12±4 hours of last dose of study medication. If not possible, the PK sample should be collected at **C** irrespective of the timing of the last study dose taken.

CCI

- y. Based on determination of positive C-SSRS results for suicidality, the participants will be discontinued from the study medication and referred to a specialist at the Investigator's discretion for further evaluation. In addition, the positive results from C-SSRS evaluation will have to be treated as an SAE and reported to the Sponsor in a timely manner.

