In this Phase 2a/b 4-arm PoC, dose-range study, treatment over CCI is intended to assess the effect of treatment with OG-6219 on efficacy, safety, and tolerability over 6 menstrual cycles.

While a previous study in cynomolgus monkeys exposed to OG-6219 for a total of CCI did not find any statistically significant changes in the mean CCI. An increase CCI in this Phase 2a/b study, if any, is expected to be fully and quickly reversible.

CCI

Also, no macroscopic or microscopic effect on bone tissue was observed in the CCI toxicology studies in rat and cynomolgus monkeys. However, no clinical experience on the effect of OG-6219 on systemic estrogen levels with longer exposure is available.

CCI

Effects on coagulation and lipid parameters as well as cardiovascular function will be monitored by serum chemistry, vital signs, and ECGs.

Participants will need to stop using any previous hormonal treatment for endometriosis as well as oral and other contraceptive treatment to enable assessment of the effect of HSD17 β 1 inhibition by OG-6219 on ERP, and menstrual regularity of the endometrium (refer to the [Table 2](#) and [Appendix 7](#)).

Embryo-fetal survival and development during the organogenesis phase of pregnancy was studied in pregnant rats and cynomolgus monkeys and no effect of OG-6219 treatment was found at the respective highest doses tested. However, as the effect of OG-6219 on fertility and early embryonic development and pre- and post-natal development has not been studied at this time, the risk of reproductive toxicity cannot be considered fully characterized. Therefore, necessary precautions to prevent pregnancy will be taken in this study. Participants will be informed about the risks to become pregnant and should not plan to become pregnant over the course of the study; only participants who are abstinent, or who are willing to reliably use an acceptable effective method for contraception as described in detail in the protocol (refer to the [Appendix 5](#)) and informed consent, or in whom safe contraception is achieved by a permanent method, will be eligible. A negative serum β -human chorionic gonadotropin (β -hCG) test prior to randomization and start of the treatment will be required, and monthly urinary pregnancy tests will be performed during the study implementation. Any pregnancy

will trigger withdrawal from study treatment, participant to expedited reporting and outcome of the pregnancy will be followed.

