OG-6219 and FOR-1011 displayed inhibition of the hERG channel potassium current with half maximal inhibitory concentration (IC₅₀) values of CCI, respectively, indicating a potential risk of QTc prolongation. Both compounds are however highly bound to plasma proteins, resulting in low free concentrations in vivo and no cardiovascular toxicity or effects on ECG were observed in the in vivo cardiovascular safety study in cynomolgus monkeys. No clinically significant ECG changes were observed in Phase 1 with intense monitoring. To manage the risk of a proarrhythmic activity, in the Phase 2a/b study, ECG recordings at Screening aim to identify and exclude participants with clinically significant cardiac abnormalities. The International Council for Harmonisation of Technical Requirements for Pharmaceuticals for Human Use (ICH) E14 Clinical Evaluation of QT/QTc Interval prolongation and proarrhythmic potential and non-antiarrhythmic drug recommends that ECG recordings be performed at time points of expected C_{max}. Therefore, ECG recordings and vital sign measurements will be performed at CCI

CCI [REDACTED] at each subsequent visit until the End of Study (EOS).

CCI [REDACTED]

[REDACTED] The ultraviolet (UV) absorbance of OG-6219 has a local maximum close to the low end of the natural sunlight wavelength range resulting in molar extinction coefficients values higher than the limit value of 1000 at wavelengths in the UVB spectrum below 305 nm. The penetration of UVB light into human skin is mainly limited to the epidermis and the clinical relevance of photochemical activation by UVB is therefore considered less important than activation by UVA for systemic drugs. The molecular structure of OG-6219 has been evaluated in silico with no alerts for photo-induced genotoxicity, chromosome damage, or photomutagenicity. In addition, no relevant distribution of OG-6219 to the skin or eyes was observed in a pre-clinical study in albino animals. Although, the binding affinity of OG-6219 to melanin has not been evaluated, the risk for phototoxicity of OG-6219 is considered minimal based on the totality of the available data and no specific precautions are therefore warranted.

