- ECG findings of QTcF prolongation of **CCI**, or a change of >60 ms from the pre-dose ECG, based on the average of triplicate ECGs
- Participants who experience suicidal ideation or attempt suicide
- Safety recommendation based on DMC / investigator/ Sponsor assessment of AEs and AESI
- If the participant becomes pregnant at any time after providing a signed ICF, the participant must be withdrawn immediately and if the participant has received at least 1 dose of experimental study treatment the participant must be followed through the pregnancy (refer to [Appendix 5](#)).
- If the participant undergoes urgent surgical procedures for endometriosis-related pain.
- The participant was erroneously included in the study (failed to meet protocol entry criteria)
- Participants whose treatment assignment has intentionally been unblinded by the Investigator
- The participant participates in another investigational study
- The participant is unable to comply with protocol requirements (eg, eDiary compliance, use of study treatment, use of rescue and prohibited medication, etc.)

Participants removed from study treatment for any reason will undergo the assessments for the discontinuation Visit (SoA, Section 1.3) and will have a Follow-up Visit to assess safety after completing 1 full cycle after the participant's last dose of study treatment.

A participant will be considered "discontinued due to an AE" if she withdraws from the study due to any AE, regardless of whether or not the AE is considered related to study treatment. If the participant withdraws from the study due to an AE, the Investigator should arrange for the participant to be followed appropriately until the AE has resolved or stabilized (in the opinion of the Investigator).

Decisions about medical care after study treatment discontinuation will be made according to Investigator's opinion.

The Investigator will document the reason(s) for treatment or study discontinuation. The Medical Monitor should be informed when a participant is withdrawn from the study.

Participants who do not wish to conceive after the last dose of study treatment should begin a new contraceptive method as soon as possible. Post-study contraceptive counseling will be provided by study site personnel in accordance with the SoA (Section 1.3).

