8.3.1 Physical Examinations

Complete physical examinations will be performed at the times indicated in the SoA (Section 1.3). These examinations will include participant's general appearance, head, eyes, ears, nose, throat, neck/thyroid, heart, lungs, musculoskeletal system, gastrointestinal system, neurological system, and skin. Special attention should be taken during screening to exclude any other pelvic pain conditions by performing an extensive anamnesis.

A focused physical examination (palpation and auscultation, if applicable) will be performed consistent with local requirements at the times indicated in the SoA (Section 1.3)

The participant's body weight and height will be recorded at the times indicated in the SoA (Section 1.3) and BMI will be calculated.

Clinically significant findings prior to dosing will be recorded on the medical history eCRF.

During the study, any clinically significant change from BC will be recorded as an AE on the AE eCRF. Clinical significance is defined as any variation in physical findings that has medical relevance and may result in an alteration in medical care. The Investigator will continue to monitor the participant until the finding is resolved or, in the judgment of the Investigator, follow-up is no longer medically necessary.

A clinical breast examination and a gynecological examination including a pelvic exam will be performed at the times indicated in the SoA (Section 1.3).

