8.3.2 Vital Signs

Vital signs include assessment of heart rate, respiratory rate, body temperature (aural measurement), and BP. Vital signs will be taken with the participant in the supine position after resting for at least 5 minutes, at the times indicated in the SoA (Section 1.3).

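### As extracted, the Schedule of Activities marks vital signs at every site visit except Discontinuation, so women who stop early have no scheduled blood pressure, respiratory rate or temperature near their last dose

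*Protocol*

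**What the plan says.** Three parts of the protocol decide whether vital signs are taken when a woman stops treatment.

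- **Schedule.** The SoA (Protocol 1.3) has the row "Vital Signs (Heart Rate, Blood Pressure, Respiratory Rate, Temperature". It is marked at all screening visits, at the on-site treatment visits, and at the start and end of the Safety Follow-up Cycle (SFC). As extracted, its Discontinuation cell is empty.
- **Timing rule.** Protocol 8.3.2 has vital signs taken supine, "after resting for at least 5 minutes, at the times indicated in the SoA". It gives no separate rule for early stopping.
- **Early stopping.** Protocol 7.2 states: "Participants removed from study treatment for any reason will undergo the assessments for the discontinuation Visit". It adds a safety Follow-up Visit one full cycle after the last dose. The same section asks for an early discontinuation visit only where possible.

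Protocol 2.3.1 bears on intent: "Effects on coagulation and lipid parameters as well as cardiovascular function will be monitored by serum chemistry, vital signs, and ECGs". A second, partly redacted sentence there begins "ECG recordings and vital sign measurements will be performed at" and ends "at each subsequent visit until the End of Study (EOS".

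Table 1 of Protocol 3.0 includes abnormal vital signs in a primary safety endpoint. SAP 8.7.4 presents seven vital-sign parameters by visit and treatment group. SAP 8.1.4 limits by-visit summaries to scheduled time points and mentions early-discontinuation data only for listings.

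**The concern.** The Discontinuation visit is the assessment closest to the last dose for a woman who leaves treatment early. Women who complete treatment have vital signs at the start of SFC; those who stop early have no matching reading scheduled. The reasons for stopping listed in Protocol 7.2 include intolerable adverse events, suspected SARS-CoV-2 infection, and raised transaminases with symptoms such as fever. In those situations blood pressure, respiratory rate and temperature are clinically informative.

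The full physical examination does not fill the gap. Protocol 8.3.1 defines it by "general appearance, head, eyes, ears, nose, throat, neck/thyroid, heart, lungs, musculoskeletal system, gastrointestinal system, neurological system, and skin", with weight and height recorded in addition, and lists none of the three measurements.

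What is at stake is the completeness of one component of a primary safety endpoint in the women who stop early. No efficacy result depends on it.

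**Working it through.** The plan gives no figure to reproduce, so the check is a reading of the table followed by a rough count.

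**Step 1: columns.** The part of the SoA that holds the vital-signs row has an 11-column header: 3 Screening + 4 Randomization and Treatment + 3 Safety Follow-up + 1 Discontinuation = 11. Discontinuation is column 11. The Timing row, in the first part of the table, places the start of TRC2 at column 6, the start of SFC at 8, "Day 14 after stopping intake of study medication" at 9 and the end of SFC at 10.

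**Step 2: rows.**

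| Row | Columns marked | Discontinuation (11) |
|---|---|---|
| Vital signs | 1–5, 7, 8, 10 | blank |
| 12-lead ECG | 1, 4, 5, 7, 8, 10, 11 | X |
| Hematology and chemistry | 1, 4, 5, 7, 8, 10, 11 | X |
| Urinalysis | 1, 4, 5, 7, 8, 10, 11 | X |
| Urine pregnancy test | 1–8, 10, 11 | X |
| Serum pregnancy test | 1, 3, 4, 5, 7, 8, 10, 11 | X |
| Adverse events | 1–11 | X |
| Full physical examination (another 11-column part) | 1, 8, 11 | X |

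The vital-signs row has all 11 cells, including an empty last one, so a shifted column does not explain the blank. Columns 6 and 9 match the two phone contacts, where vital signs cannot be taken. Discontinuation is then the only in-person column without them. The focused physical examination is also blank at Discontinuation, but the full examination replaces it there; nothing replaces vital signs.

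**Step 3: what is lost.** Of the seven parameters in SAP 8.7.4, heart rate can be read from the ECG, and weight and BMI come from the full physical examination. That leaves 7 − 3 = 4 with no scheduled source at Discontinuation: systolic pressure, diastolic pressure, respiratory rate and temperature.

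**Step 4: how many women.** SAP 4.3 gives 380 randomized, 95 per group, and a 10% dropout allowance. If treatment discontinuation equals that allowance, 0.10 × 380 = 38 women, or 0.10 × 95 = 9.5 per group. The allowance is a sample-size input, not a forecast of treatment discontinuation, so a range is needed:

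| Assumed discontinuation | Women | If half attend the visit (assumption) |
|---|---|---|
| 5% | 0.05 × 380 = 19 | 9.5 |
| 10% | 38 | 19 |
| 20% | 0.20 × 380 = 76 | 38 |

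**The case against.** The strongest objection is that this rests on one empty cell in a machine-read table that is visibly damaged. Header widths differ between its parts, several footnote markers are misread, and the plasma PK row shows a single mark although its footnote requires samples at all dosing-period visits. The Timing row used in Step 1 itself comes from a part with a 12-column header, in which the start of SFC sits under the treatment band. These points stand as reasons for caution, and a lost mark cannot be excluded. They do not account for a blank in a row whose cell count matches its own header and whose neighbours are marked in that column. The C-SSRS row, in another part with a 12-column header, is not relied on.

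A second objection is that the reading is covered elsewhere. The synopsis frames the primary safety summary as change from baseline to end of study. Women taken off treatment get a Follow-up Visit, and vital signs are marked at the end of SFC. Clinically significant abnormalities are reportable as adverse events. This stands in part and is why the point is minor. But a visit one full cycle later does not describe a woman's state near her last dose, and an abnormality that is not measured may not be reported.

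Three stronger readings are tempting, and the documents support none of them:

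- **No vital signs at all after stopping.** The later Follow-up Visit and measurements prompted by adverse events remain.
- **A proven omission, or a deliberate choice.** The first Section 2.3.1 statement names no visit, and the second has its time points redacted. Together they make an omission more likely but are weak evidence.
- **A Discontinuation reading would certainly reach no group summary.** That is an inference from the general rule in SAP 8.1.4, which also affects other by-visit safety data.

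**Conclusion.** The point holds as a minor gap in safety scheduling, provided the source table shows the same blank cell. Blood pressure, respiratory rate and temperature then have no scheduled measurement near the last dose in women who stop early, because Sections 7.2 and 8.3.2 both defer to the SoA and no other section schedules them.

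The number of women affected is unknown. About 38 of 380 applies only if treatment discontinuation matches the SAP's 10% dropout allowance, and the figure falls if some do not attend. Each would lack one set of readings, not all her vital-sign data. Sample size, power and the primary efficacy analysis are unaffected.

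**What to change.** Check the vital-signs row in the source table. If the Discontinuation cell is blank, add an X. This costs a few minutes at a visit already held, plus a minor amendment or a site memo.

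Optionally, add one sentence to SAP 8.7.4 stating that Discontinuation readings enter a last-on-treatment or end-of-treatment vital-sign summary by treatment group. Without it, SAP 8.1.4 leaves it unclear whether the added reading would appear anywhere but in listings.

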2.0 INTRODUCTION

Organon is developing OG-6219 (formally known as FOR-6219) for the treatment of moderate to severe endometriosis-related pain (ERP). Organon acquired Forendo on 13 December 2021 and is now the owner and developer of OG-6219 as a novel hydroxysteroid-17 β -dehydrogenase type 1 (HSD17 β 1) enzyme inhibitor for the treatment of moderate to severe pain in endometriosis.

The main source of circulating estrogens in pre-menopausal women is the ovary. However, estrogens are also synthesized in peripheral tissues. Local biosynthesis of biologically active estradiol (E2) within the endometriotic lesions is thought to play a central role in the pathophysiology of endometriosis.¹⁻³ In general, only a very small proportion of E2 and the androgens (testosterone, and dihydrotestosterone [DHT]), produced intracellularly by the steroidogenic enzymes of the intracrine pathways diffuse into the circulation, thus avoiding systemic effects. This intratissue hormone metabolism is known as intracrinology or intratissue hormone metabolism and is considered an important part of the endocrine control at the end organ level.^{4,5}

[figure not shown]
Hydroxysteroid-17 β -dehydrogenases (HSD17 β s) are a family of enzymes that catalyse the interconversion between the active and inactive forms of specific steroidal hormones on the final steps of their biosynthesis.⁶⁻⁸ In mammals, there are at least 15 HSD17 β 1 enzymes and the nomenclature of these enzymes follow their discovery; the majority of these belong to the short-chain dehydrogenase/reductase (SDR) family.⁹

In the late 1980's, the human HSD17 β 1 was the first member of the HSD17 β enzyme family to be cloned and sequenced.^{9,10} Among the HSD17 β enzymes, HSD17 β 1 possesses the highest specificity for steroids as a substrate and the highest catalytic activity for converting the low active estrone (E1) to highly active E2 (17 β estradiol; E2) and is always involved in the final E1 to E2 activation step.^{11,12} This occurs in target cells where the estrogenic effect is exerted via the estrogen receptor.

The hydroxysteroid-17 β -dehydrogenase type 2 (HSD17 β 2) catalyzes the opposite reaction converting highly active E2 to the less active E1. Thus, HSD17 β 1 and HSD17 β 2 regulate the balance between the highly active E2 and less active E1, which has shown to be essential for the regulation of intratissue estrogen concentrations both in the endometrium and endometriosis lesions (implants).^{1,13} (Figure 2).

Figure 2 HSD17 β 1 and HSD17 β 2 enzymes regulate the balance of the low active E1 and highly active E2 in endometriotic lesions

Abbreviations: HSD17B1=Hydroxysteroid-17 β -dehydrogenase type 1; HSD17B2=Hydroxysteroid-17 β -dehydrogenase type 2.

An imbalance between HSD17 β 1 and HSD17 β 2 in endometriotic lesions as compared to normal endometrium has been demonstrated.^{2,14,15} This is attributed to the failure of upregulation of HSD17 β 2 in endometriotic lesions due to their functional progesterone resistance^{16,17} and therefore contributing to the increased E2 levels, ie, more estrogenic environment in the endometriotic lesions.

HSD17 β 1 expression is seen in the eutopic endometrium throughout the cycle.¹⁸ The HSD17 β 1 and HSD17 β 2 are both expressed in endometrium and endometriotic implants²⁰; however, there is an imbalance between HSD17 β 1 and β 2 in endometriotic lesions as compared to normal endometrium (eutopic endometrium).^{2,14,15}

In a recently published study²¹, in which protein levels of different enzymes were determined in both eutopic endometrium and endometriotic lesions, eutopic endometrium presented higher levels of aromatase, compared to steroid sulfatase (STS) or HSD17 β 1, while endometriotic lesions had superior levels of STS and HSD17 β 1.

The pharmacological action of the novel HSD17 β 1 enzyme inhibitor OG-6219, is based on its potent and selective binding to HSD17 β 1²² and ability to inhibit E2 production from E1.^{23,24} OG-6219 is not expected to interfere with the biological effects of circulating E2 because the putative mechanism of action is based on its ability to inhibit local conversion of E1 to E2 in endometriotic lesions without evidence of any off-target effects. Furthermore, OG-6219 has no intrinsic estrogenic or antiestrogenic activity, and no agonist or antagonistic activity at the progesterone receptor B. Screening in vitro for activity with 13 enzymes and 74 different binding assays further confirmed the absence of off-target effects with OG-6219.²⁵⁻²⁷

CCI

CCI. As proof of concept (PoC), HSD17 β 1 inhibitors have demonstrated the ability to reduce the lesions size and number in a marmoset monkey endometriosis model²⁸ and inhibit the E2 formation in human endometriotic lesions ex vivo.²⁹ These data as well as other studies,^{30,31} demonstrate the importance of the local E2 metabolism independent from the ovarian steroidogenesis and suggests HSD17 β 1 as a valid target for the treatment of ERP. An inhibitor of HSD17 β 1 should therefore be suitable in preventing the local synthesis of E2 in endometriotic lesions^{2,15,20} and may have therapeutic activity in ERP.

